15.2.2. Efficacy Population

The efficacy population will consist of all subjects who are randomized, have received at least one dose of study drug, and have a Baseline and at least one post-Baseline efficacy measurement in PANSS or CGI-S. Subjects will be included in the population regardless of any protocol deviation. The efficacy population will be the primary population for the efficacy analyses. Subjects will be analyzed according to the treatment to which they are randomized.

15.2.3. Per Protocol Population

The per protocol (PP) population will consist of all efficacy population subjects who satisfy the following conditions:

- Have 14 days or more overall exposure to study drug
- Have no important protocol deviations, determined by blinded data reviews prior to database lock

Selected efficacy endpoints will be analyzed using the PP population. Subjects will be analyzed according to the treatment to which they are randomized.

15.3. Data Analysis

15.3.1. Subject Disposition

Subject disposition will be summarized by the actual treatment group (if applicable) and overall for all subjects. The number and percent of subjects, who are screened, screen-failed, randomized, received study drug, and completed or discontinued early from the double-blind treatment period (including reasons for discontinuation) will be presented.

As exploratory analysis, the time-to-discontinuation (any reason) by treatment will be summarized descriptively and will also be tested with log-rank statistic and presented by a Kaplan-Meier plot.

15.3.2. Study Drug Exposure and Compliance

Duration of exposure and compliance will be summarized by treatment group for the safety population.

Duration of exposure (in days) will be calculated as: last dose date - first study dose date + 1. Duration of exposure will be summarized both as a continuous variable and categorically:

- Number and percentage of subjects with the study drug exposure $\geq 1, \geq 14, \geq 28, \geq 42, \geq 90, \geq 120, \geq 150, \geq 180, \geq 270$, and ≥ 360 days;
- Number and percentage of subjects with the study drug exposure for 1 - 13, 14 - 27, 28 - 41, 42 - 89, 90 - 119, 120 - 149, 150 - 179, 180 - 269, 270 - 359, and ≥ 360 days

Percent compliance will be calculated overall for the treatment period as: (number of capsules taken / number of capsules should have been taken) $\times 100\%$. Non-compliance is defined as less than 75% or more than 125% non-missing compliance for the treatment period. Subjects with missing compliance will not be classified as non-compliant. Percent compliance will be summarized both as a continuous variable and categorically (i.e. number and percentage of subjects in each compliance category: < 75%, 75% - 125%, > 125%, and missing).

Mean daily dose will be calculated for the treatment period as the cumulative dose (mg) of SEP-363856 or quetiapine XR (depending upon randomization) divided by the duration of exposure (in days), where cumulative dose is the sum of all doses a subject received during the treatment period. Modal daily dose will be determined as the daily dose that is taken for the most time (in terms of number of days) among all doses taken. Both mean daily dose and modal daily dose will be summarized.

15.3.3. Important Protocol Deviations

Important protocol deviations (IPDs) will be identified and documented based on blinded review of data listings. The IPD categories may include, but may not be limited to:

- Did not meet important inclusion and/or exclusion criteria.
- Received prohibited medication.
- Overall double-blind compliance rate < 75% or > 125%.

IPDs will be identified for all randomized subjects and presented in a data listing. The number and percentage of subjects within each IPD category will be summarized for the safety population.

15.3.4. Demographic and Baseline Characteristics

Basic demographics (e.g. age, gender, race, ethnicity, etc.) will be summarized for all screened subjects by randomization status (i.e. randomized vs. not randomized). Demographic and baseline characteristics will be summarized for each defined analysis population by treatment group and overall.

Medical and psychiatric history will be coded using the Medical Dictionary for Regulatory Activities (MedDRA) and will be summarized by treatment for the safety population by presenting the number and percentage of subjects with at least one condition in each system organ class (SOC) and preferred term (PT).

15.3.5. Efficacy Analyses

Efficacy data will be summarized descriptively by treatment for the efficacy population.

The observed values of PANSS total score and subscale scores (positive, negative, and general psychopathology), CGI-S score, BNSS total score, MADRS total score, BACS composite score, ESS total score, SLOF total and subscale scores, EQ-5D-5L VAS, index score and dimension score, UPSA-B total score, and MSQ score, at Baseline and each scheduled post-Baseline visit, will be summarized descriptively. Changes from Baseline in these efficacy measures as well as changes from baseline in tobacco use and cotinine concentrations, will be summarized at each scheduled post- Baseline visit.

PANSS total score and CGI-S score data will also be summarized by age, sex, race, number of prior hospitalizations for treatment of schizophrenia, duration of schizophrenia, geographic region, and country.

The proportion of subjects who achieve a response, defined as a 20% or greater improvement (i.e. decrease) in PANSS total score from the Baseline, will be calculated for each scheduled visit and the Week 52 last-observation-carried-forward (LOCF). The proportion of subjects who achieve a response, defined as a 30% or greater improvement (i.e. decrease) in PANSS total score from the Baseline, will be summarized similarly. As exploratory analyses, PANSS total score and subscale scores, CGI-S score, BNSS total score, and MADRS total score will be analyzed using a mixed model for repeated measures (MMRM) under the missing-at-random (MAR) assumption. Under this assumption, the efficacy outcome of subjects in each treatment group after early discontinuation will exhibit the same future evolution as subjects in the same group remaining in the study. The MMRM model will include fixed factors for treatment, visit as a categorical variable, country, and treatment-by-visit interaction, and include Baseline score as a covariate. An unstructured covariance matrix will be used to model the within-subject correlation. Kenward-Roger approximation will be used to calculate the denominator degrees of freedom. The main estimator of the efficacy estimand is the least squares (LS) mean difference in each score change from Baseline at Week 52 from the analysis model of observed repeated measures data.

In case the model above fails to converge, a spatial exponential covariance structure and a spatial power covariance structure will be assumed sequentially. The first covariance structure to yield convergence will be used in the analysis. These analyses will be based on the observed data only. Missing data will not be imputed.

Sensitivity analyses may be conducted to assess the impact of missing data on the PANSS total score and CGI-S score analysis results by deviating away from the MAR assumption; however, all efficacy analyses are exploratory in this safety study.

Relapse

Relapse will be identified programmatically and manual data review using the pre-defined criteria (specified below). The rate of relapse will be calculated as the proportion of subjects with

a relapse in the 52-week period out of the efficacy population, along with the 95% confidence interval. The time-to-relapse will be summarized descriptively and will also be presented by a Kaplan-Meier plot, with log rank test statistic.

Relapse will be defined as the earliest occurrence of any of the following:

- Worsening of > 30% PANSS total score from Baseline (Day 1) and a CGI-S score > 3.
- Hospitalization for worsening of psychosis.
- Emergence of suicidality, homicidality and/or risk of harm to self or others.
- Discontinuation from the study due to exacerbation of the underlying illness of schizophrenia.

The frequency of hospitalization due to relapse will be summarized descriptively by treatment.

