8.2. Subject Exclusion Criteria

To qualify for participation, subjects must not meet any of the following exclusion criteria:

1. Subject was hospitalized for a psychiatric illness within the 8 weeks prior to Screening.
2. Subject has a current DSM-5 diagnosis or presence of symptoms consistent with a DSM-5 diagnosis other than schizophrenia. Exclusionary disorders include but are not limited to alcohol use disorder (within past 12 months or for a total of ≥ 10 years during the subject's lifetime), substance (other than nicotine or caffeine) use disorder within past 12 months or for a total of ≥ 10 years during the subject's lifetime, major depressive disorder, schizoaffective disorder, bipolar I or II disorder, obsessive compulsive disorder, and posttraumatic stress disorder. Symptoms of mild to moderate mood dysphoria or anxiety are allowed so long as these symptoms are not the primary focus of treatment.
3. Subject is judged to be resistant to antipsychotic treatment by the Investigator, based on failure to respond to 2 or more marketed antipsychotic agents within a 1-year period prior to Screening, given at adequate dose as per labeling, for at least 4 weeks.
4. Subject answers "yes" to "Suicidal Ideation" Item 4 (active suicidal ideation with some intent to act, without specific plan) or Item 5 (active suicidal ideation with specific plan and intent) on the C-SSRS assessment at Screening (i.e., in the past one month) or at Baseline (i.e., since last visit).
5. Subject is at significant risk of harming self or others based on Investigator's judgment.
6. Subject has attempted suicide within 6 months prior to Screening.
7. Subject has received treatment with a psychotropic medication or herbal supplement within 3 days or 5 half-lives (whichever is longer) prior to randomization or anticipates the need for psychotropic medications or herbal supplements during their participation in this study, with the exception of the medications specified in [Section 10.3.5](#). The following medications have additional washout requirements as specified below:
 - Monoamine oxidase inhibitors (MAOIs) must be discontinued at least 28 days prior to randomization.
 - Fluoxetine must be discontinued at least 28 days prior to randomization.

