2.1.3. OTHER EFFICACY OBJECTIVES

The other efficacy objectives are:

- To evaluate the long-term effectiveness of SEP-363856 and Quetiapine XR using the
 - Positive and Negative Syndrome Scale (PANNS)
 - Clinical Global Impression-Severity (CGI-S) scale
 - Brief Negative Symptom Scale (BNSS)
 - Montgomery-Asberg Depression Rating Scale (MADRS)
- To evaluate the maintenance efficacy of SEP-363856 and Quetiapine XR (including time to relapse, rate of relapse and frequency of hospitalization due to relapse)
- To evaluate adherence to study treatment based on time to all cause discontinuation
- To evaluate the effects of SEP-363856 and Quetiapine XR on daytime sleepiness as measured by the Epworth Sleepiness Scale (ESS)
- To assess the effects of SEP-363856 and Quetiapine XR on cognition as measured by the Brief Assessment of Cognition in Schizophrenia (BACS)
- To explore the effects of SEP-363856 and Quetiapine XR on functional capacity as measured by the University of California San Diego (UCSD) Performance-Based Skills Assessment – Brief Version

Document:

CCI

Author:

PPD

Version Number:

0.6

Version Date:

30JAN2023

Template No.: CS_TP_BS016 Revision 6

Reference: CS_WI_BS005

Effective Date: 02Dec2019

(UPSA-B)

- To evaluate the effects of SEP-363856 and Quetiapine XR on function as measured by the modified Specific Level of Functioning Scale (SLOF)
- To evaluate the effects of SEP-363856 and Quetiapine XR on health-related quality of life as measured by the EuroQol-5D-5L (EQ-5D-5L)
- To evaluate medication satisfaction as measured by the Medication Satisfaction Questionnaire (MSQ)
- To explore the impact of SEP-363856 on nicotine use

CCI

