5.2. EFFICACY (EFF) POPULATION

The efficacy population will consist of all subjects who are randomized, have received at least one dose of study drug, and have a Baseline and at least one post-Baseline efficacy measurement in PANSS or CGI-S administered within 9 days after the last dose of study drug. Subjects will be included in the EFF population regardless of any protocol deviation. The EFF population will be the primary population for the efficacy analyses. Subjects will be analyzed according to the treatment to which they are randomized.

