16. EFFICACY OUTCOMES

Unless otherwise specified, the efficacy analysis and summary tables will include the following columns:

Document: CCI

Author: PPD

Version Number: 0.6

Version Date: 30JAN2023

Template No.: CS_TP_BS016 Revision 6

Reference: CS_WI_BS005

Effective Date: 02Dec2019

SEP-363856 50 to 100 mg/day, Quetiapine XR 400 to 800 mg/day.

All analyses of the efficacy variables will be based on the EFF population and, for selected variables/analyses, the PP population by the randomized treatment group.

Efficacy data collected after an emergency treatment unblinding (see protocol Section 7.2.3) will not be used in any statistical analysis. These data will be listed in data listings only.

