16.2.10. TOBACCO USE

Tobacco use is assessed at these study visits: Visit 2, Visit 7, Visit 10 and Visit 17. Tobacco use data will be summarized descriptively by treatment group and visit.

For each tobacco type, the amount being used at Week 12/Visit 7, Week 24/Visit 10, Week 52/Visit 17 and LOCF in comparison with the amount being used at Baseline will be classified as “increased”, “decreased”, or “unchanged” for every subject, based on the reported amount used in a given period. If a subject quit using a particular type of tobacco since Baseline, the amount used for that tobacco type will be classified as “decreased”. If a subject newly started or restarted using a particular type of tobacco since Baseline, the amount used for that tobacco type will be classified as “increased”.

Then for subjects whose changes in amount for all tobacco types between Baseline and each scheduled post-Baseline visit (Week 12/Visit 7, Week 24/Visit 10, Week 52/Visit 17 and LOCF) are not in opposite directions, a subject’s overall tobacco consumption at each scheduled post-Baseline visit in comparison with Baseline will be classified as “increased”, “decreased”, or “unchanged” based on the following:

- If the change in amount for each tobacco type is either “increased” or “unchanged”, the subject’s overall consumption will be classified as “increased”.
- If the change in amount for each tobacco type is either “decreased” or “unchanged”, the subject’s overall consumption will be classified as “decreased”.
- If the change in amount for all tobacco types is “unchanged”, the subject’s overall consumption will be classified as “unchanged”.

The number and percentage of subjects in each overall consumption amount change category will be summarized by treatment group.

In addition, for subjects who reported using “Cigarettes” at either Baseline or each scheduled post-Baseline visit (Week 12/Visit 7, Week 24/Visit 10, Week 52/Visit 17 and LOCF) or at both time points, the number of cigarettes used per day will be derived for both time points. The following conversion will be applied if necessary:

- Amount: 1 Pack = 20 Cigarettes.
- Time period: 1 Week = 7 Days; 1 Month = 30 Days.

Document: CCI

Author: PPD

Version Number: 0.6

Version Date: 30JAN2023

Template No.: CS_TP_BS016 Revision 6

Reference: CS_WI_BS005

Effective Date: 02Dec2019

The amount of cigarette used per day and the change from Baseline values will be summarized by treatment group and visit.

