16.2.11. PLASMA COTININE CONCENTRATIONS

Plasma cotinine levels are assessed at these study visits: Visit 2, Visit 7, Visit 10 and Visit 17.

The observed plasma cotinine levels and change from Baseline values at each post-Baseline scheduled visit (Week 12/Visit 7, Week 24/Visit 10, Week 52/Visit 17) will be summarized descriptively by treatment group and visit.

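### Plasma cotinine change is summarised without separating tobacco users from non-users, so the mean is scaled down by the user share and the median may be uninformative

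*Protocol*

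**What the plan says.** Both documents list nicotine use among the other efficacy objectives: "To explore the impact of SEP-363856 on nicotine use" (SAP 2.1.3; the same objective is in Protocol 5.3). Plasma cotinine is a named endpoint for it.

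For the analysis, Protocol 15.3.5 states that "changes from baseline in tobacco use and cotinine concentrations, will be summarized at each scheduled" post-Baseline visit. SAP 16.2.11 repeats this: "The observed plasma cotinine levels and change from Baseline values at each post-Baseline scheduled visit" are summarised descriptively by treatment group and visit. No test or model is planned for cotinine.

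The population follows from SAP section 16: "All analyses of the efficacy variables will be based on the EFF population". SAP 5.2 requires randomisation, at least one dose, and that subjects "have a Baseline and at least one post-Baseline efficacy measurement in PANSS or CGI-S" within a set time of the last dose. Tobacco use plays no part.

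Entry does not depend on tobacco use either. Protocol 8.2 excludes "substance (other than nicotine or caffeine) use disorder within past 12 months", so nicotine is carved out of the exclusion and users and non-users can both enrol.

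SAP 16.2.10 treats cigarettes differently. Only "for subjects who reported using “Cigarettes” at either Baseline", at the post-Baseline visit, or at both, is it planned that "the number of cigarettes used per day will be derived for both time points".

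**The concern.** A subject who never uses tobacco during the study should have cotinine near zero throughout and so a change near zero. Such a subject says little about whether treatment alters nicotine intake, yet counts fully in the mean and median. The planned summary therefore mixes two quantities: how many subjects use tobacco, and how much the users' exposure changes. A modest mean change could reflect a small effect in many users or a larger effect in few.

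The mix also matters between arms. Randomisation is stratified by country only (Protocol 7.2.1, SAP 3.2), so the user share can differ between arms by chance. The mean changes would then differ even if users in both arms changed by the same amount.

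What is at stake is how readable one exploratory result is. Cotinine is nevertheless the only laboratory measure listed for the nicotine objective. It is also the only quantitative one that covers all tobacco types, because SAP 16.2.10 quantifies cigarettes alone and classes other types as increased, decreased or unchanged.

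**Working it through.** The documents give no expected cotinine effect, standard deviation or user share, so there is no planned figure to reproduce. The shares and effects below are assumptions, shown as ranges.

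**Mean.** Let q be the share of subjects who never use tobacco, with change 0, and let m be the users' mean change.

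All-subject mean change = q × 0 + (1 − q) × m = (1 − q) × m.

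This is exact if non-users stay at zero. It is approximate if they are only near zero or if some start tobacco.

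**Median.** The median is below zero only if more than half of all subjects fall, that is if (1 − q) × P(fall, given user) > 0.5. The share of users who must fall is therefore more than 0.5 / (1 − q). The same holds for rises. At q = 0.3 this is 0.5 / 0.7 = 71.4%. At q above 0.5 the required share exceeds 100%, so the median is zero for any effect. At exactly 0.5 it is zero unless every user moves the same way.

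**Sample medians.** 4,000 samples of 80 subjects were simulated per setting, with users' change Normal(−d, 1) in SD units and non-users at exactly 0. The size of 80 is the number expected to complete one year on SEP-363856 (Protocol 15.1).

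| Assumed non-user share q | Mean retained, 1 − q | Users who must move the same way, 0.5/(1 − q) | Chance sample median is exactly 0, d = 0.5 SD | Same, d = 1 SD |
|---|---|---|---|---|
| 0.1 | 90% | 55.6% | 0.01 | 0.00 |
| 0.2 | 80% | 62.5% | 0.14 | 0.00 |
| 0.3 | 70% | 71.4% | 0.57 | 0.04 |
| 0.4 | 60% | 83.3% | 0.92 | 0.43 |
| 0.5 | 50% | all | 1.00 | 0.90 |
| 0.6 | 40% | not possible | 1.00 | 1.00 |

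The mean column does not depend on the effect size. The median columns depend heavily on both effect and share.

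**Imbalance between arms.** If users change by m in both arms and the user shares are p1 and p2, the difference in all-subject means is (p1 − p2) × m. With an assumed m of −40 ng/mL and shares of 60% and 50%, the means are −24 and −20, a difference of −4 with no difference among users.

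**Numbers left in a user table.** Of 80 completers on SEP-363856, users would number 80 × (1 − q): 56, 48, 40 or 32 at q = 0.3, 0.4, 0.5 or 0.6.

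**The case against.** The other side has several fair points.

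- **The median.** A reader might infer that the median change will be zero whatever treatment does. The documents do not support that, because they give no user share. With 20% non-users and a 0.5 SD fall in users, the chance of a zero sample median is 0.14. With 30% non-users and a 1 SD fall it is 0.04.
- **Other planned output.** The SAP's output conventions (Appendix 1) cover quartiles, SD and range as well as mean and median. If users change by an assumed mean of −40 with SD 100, the lower quartile over all subjects is −40 at 50% users and about −77 at 70%, so an effect could show there. Observed cotinine levels and tobacco use are also summarised by arm, which would make an imbalance in user share visible. This reduces the harm, but the reader must still infer the users' change.
- **Legitimacy of the all-subject summary.** It keeps the randomised groups intact and counts uptake. SAP 16.2.10 foresees subjects who start or restart tobacco, so a Baseline non-user need not contribute zero. This stands, and is why that summary should stay.
- **The cigarette precedent.** A reader might infer that the SAP has a general users-only rule and that cotinine breaks it. It has none: cigarettes per day is a type-specific quantity, and the overall-consumption classification in the same section is not restricted to users. The contrast with cigarettes supports adding a split but does not make its absence an error.
- **Borrowing that rule.** It would be natural to copy the cigarette rule and select on use at Baseline or at the visit. Use at the visit is reported after randomisation and can itself be affected by treatment. The subset would then change from visit to visit, and its composition could differ between arms because of the drug.
- **Consequence.** Protocol 15.3.5 describes all efficacy analyses as exploratory, and no planned power is lost. This stands and limits the weight of the point.

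**Conclusion.** The point holds in a limited form. Cotinine change is summarised in the efficacy population without separating users from non-users. To the extent that non-users stay near zero, the mean is the users' mean change multiplied by the user share, whatever the effect: 70%, 50% or 40% of it at assumed non-user shares of 30%, 50% or 60%. The median is zero if non-users are half or more. Below that it depends on the effect and on a share the documents do not state, so nothing firmer can be said about it.

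It would also go too far to infer that the nicotine objective cannot be addressed as planned. Tobacco-use categories and cigarettes per day remain, and the all-subject cotinine summary answers a legitimate question. What is missing is the cotinine change among users. On an exploratory, descriptive endpoint, that is a cheap improvement and not a flaw affecting the trial's conclusions.

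**What to change.** In SAP 16.2.11, keep the all-subject summary. Add cotinine level and change from Baseline by arm and visit in two subsets fixed before treatment: subjects who report any tobacco use at Baseline (Visit 2), and subjects who report none. In the second subset a rise would indicate uptake. Do not define either subset by use at a post-Baseline visit.

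No new data are needed, since tobacco use and cotinine are both collected at Visits 2, 7, 10 and 17 (SAP 16.2.10 and 16.2.11). The cost is one further descriptive table with smaller numbers per cell. It also relies on self-reported Baseline use, so users who do not report it would be placed among the non-users. The Baseline cotinine levels shown for that subset would help to reveal this.
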